6.4.2.2 PATIENTS SCHEDULED FOR ELECTIVE SURGERY WITH OLV

Patients scheduled for elective surgery will receive medical care according to the hospital's established standards. Before anesthesia induction, study team will re-evaluate whether all in- and exclusion criteria are appropriately met (e.g. still intubated). Patients are considered "enrolled" when written informed consent has been obtained and all in- and exclusion criteria are appropriately met.

After arrival in the induction room, patients will be connected to the appropriate monitors for routine patient care. Additionally, patients will be asked to sit up and have the electrode belt of PulmoVista 500 fitted to their thorax according to the IfU. Investigational device is set up and connected to the patient and related devices.

Before and during pre-oxygenation of the patient, study personnel will start and test recording of the data. Anesthesia induction, placement and confirmation of correct placement of the DLT / bronchial blocker will be performed according to the hospital's established standards of care.

In patients who require independent lung ventilation during their surgical procedure, EIT measurements shall be performed during normal (both lungs) and single-lung ventilation after induction of anesthesia before start of surgery. According to standard of care correct positioning of the DLT respectively of the bronchial blocker will be tested by switching between normal ventilation and single-lung ventilation (right and left lung will be tested independently).

During the anesthesia induction, study personnel will note the time of particular events (e.g. start of induction, mask ventilation, intubation, clamping left/right) by using the clock on PulmoVista 500. The physician in charge of the anesthesia will be asked to allow uninterrupted baseline readings of at least 2 minutes after successful intubation and to keep the left and right lumen of the DLT clamped for at least 1 minutes each to ensure stable recording of the data. Each step of the testing of correct placement of the DLT or the bronchial blocker will be marked in PulmoVista 500 before the conduct of this step.

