7 STATISTICAL CONSIDERATIONS

7.1 SAMPLE SIZE, DROP-OUT-RATES, LEVEL OF SIGNIFICANCE AND POWER OF THE CLINICAL INVESTIGATION

Primary Endpoint (Efficacy)

Based on former porcine trials⁷ with PulmoVista 500 and data from clinical studies with other EIT devices the sample size was calculated using the program G*Power 3.1.9.2.

An α -error of $p = 0.05$ and a power = 0.9 in a two-sided testing resulted in a sample size of 68 patients. With this sample size a difference of 0.1 of the mean cross-correlation coefficient shall be detected, i.e. the true value of a calculated mean of 0.8 will not be smaller than 0.7 and not be larger than 0.9 with the given p-value and power under the assumption of a standard deviation of less than .25.

Accounting for 15 % potential drop-outs 80 patients shall be enrolled in the study.

Secondary Endpoint (Efficacy)

Based on former porcine trials with PulmoVista 500 and data from clinical studies with other EIT devices the sample size was calculated using the program G*Power 3.1.9.2. An α -error of $p = 0.05$ and a power = 0.9 in a two-sided testing resulted in a sample size of 22 patients. With this sample size a difference of 0.1 of the proportion between reference and investigated variable shall be detected.

Accounting for 15 % potential drop-outs 25 patients shall be enrolled in this subgroup of the study.

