7.2 STATISTICAL DESIGN

Null-Hypothesis

The PulmoVista 500 is not capable of continuously monitoring ventilation.

Primary Endpoint (Efficacy)

To assess the capability of PulmoVista 500 for continuous monitoring of ventilation and its changes at different points in time during varying states of regional ventilation, the cross-correlation function (CCF) between global tidal impedance (EIT) waveforms and global tidal volume (ventilator) curves will be evaluated.

- To refute the null-hypothesis of this trial it must be shown that the global tidal impedance waveforms and the global tidal volume curves correlate

⁷ Fischer E, Gremse F. Assessment of the capability of PulmoVista® 500 to continuously monitor regional ventilation distribution and its changes over time. An Animal Study. FINAL STUDY REPORT. PulmoVista 500-30022. Aix Scientifics. 2016-01-27

significantly, i.e. that the correlation scores are significantly different from zero.

- If the null-hypothesis is refuted the capability of PulmoVista 500 is assumed to be a valuable diagnostic device for long-term monitoring of mechanical ventilation.

The mean value of the intra-subject cross-correlation function (CCF) between global impedance (EIT) waveforms and global volume (ventilator) curves will be determined.

Secondary Endpoint (Efficacy)

To assess the capability of PulmoVista 500 to detect regional changes of ventilation it shall be tested, whether EIT can correctly differentiate between normal and single-lung ventilation.

- To refute the null-hypothesis of this trial it must be shown that the regional information about tidal impedance variation matches the clinical changes from normal to single-lung ventilation, i.e. that EIT detects ventilation vs. no ventilation in each lung.
- If the null-hypothesis is refuted the capability of PulmoVista 500 is assumed to be a valuable diagnostic device for detecting regional ventilation changes during long-term monitoring of mechanical ventilation.

The diagnostic output of the EIT measurements will be compared with clinical ventilation settings in a 2x2 table.

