5.6 SECUNDARY ANALYSIS

5.6.1 Efficacy

- To demonstrate the ability of PulmoVista 500 to visualize regional ventilation changes, a quantitative evaluation is performed by calculating the cross-correlation coefficients between the impedance waveforms of PulmoVista 500 and the ventilator volume waveforms of OLV patients. The evaluation is carried out as in the primary analysis.
- In addition, a qualitative evaluation of the regional changes will be carried out. To do so, three blinded raters compare the corresponding sections of all OLV patients independently. Based on the information from the PulmoVista 500 video sequence provided, the raters evaluate which of the two halves of the lung is ventilated. The results are entered patient-related (pseudo-patient number) in the following table by the rater:

Pseudo-Patnr.	Valuation	
1	1	
2	2	
3	0	
4	1	
.	.	

Description of valuation:	0	not assessable
	1	right ventilated / left blocked
	2	left ventilated / right blocked

Tab. 1: Example of table for the qualitative evaluation of the OLV patients and the associated rating

The PulmoVista 500 video sequences to be assessed are created according to a workflow (see Appendix 7.3 Workflow for the creation of OLV videos) and made available to the raters. The pseudo-patient numbers are randomly generated by lot. These three tables of the raters will be merged into the KKS. A decision is considered positive or negative if at least two raters have come to the same result. In the opinion of one or more raters, is it not possible to judge the waveform (Code 0), the following assignment applies:

1x not evaluable & 2x same decision -> clear assignment in the table,
 1x not assessable & unequal decision of the remaining 2 raters -> drop out,
 2x or 3x not evaluable -> drop out.

A 2x2 Table will be created in the following form from the 3 tables of the raters (one of each rater):

Reference	Evaluation of the raters (with information provided by PulmoVista 500)	
	right ventilated / left blocked	left ventilated / right blocked
right ventilated / left blocked	a	b
left ventilated / right blocked	c	d

Tab. 2: Table for the accordance of rater and reality of the OLV patients

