7.3 WORKFLOW FOR THE CREATION OF OLV VIDEOS

This workflow describes the creation of the video sequences which are used to assess the capability of PULMO VISTA 500 to monitor regional changes during mechanical ventilation within the OLV-subgroup.

Software:

- Dräger EIT Simulation Tool
- Camtasia Recorder 8
- Camtasia Studio 8

Workflow:

1. Identify the acquisition dates and the patient/site IDs of all OLV patients
2. Identify relevant markers which are set prior and post the induction of one lung ventilation
 - a. document time-stamp of each marker
3. Load EIT-data into *Dräger EIT Simulation Tool*
 - a. Select the “Folder” which contains the acquisition date
 - b. Select the “Subfolder” which contains the relevant patient ID (xx_yyy)
 - c. Select the start-“File” which includes the relating “PRE-Marker”
 - d. Select the “Sequence to file” which includes the relating “POST-Marker”
4. Start *Camtasia Recorder 8*
5. Adjust the recording window according to the size of the “Main”-view
6. Start the simulation within *Dräger EIT Simulation Tool*
7. Start the recording
8. After the simulation has completed one entire loop of simulation, stop the recording
9. Save the recorded video file (use site and patient ID, as well as date of recording) for the definition of the file name
10. Load recorded video file into *Camtasia Studio 8*
11. Crop video sequence according to the previously identified time-stamps of the pre and post markers (the video sequence now contains only the EIT information between the two markers)
12. Process the final video sequence as MP4-file
13. Save the MP4-file containing the respective site and patient ID as well as the date of video processing.

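### Both lungs are tested in turn in each OLV patient, but the blinded rating appears to take one side per patient, so sensitivity and specificity each rest on about half the patients

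*SAP*

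**What the plan says.** - **Recording (Protocol 6.4.2.2).** EIT is recorded after induction and before surgery. Tube or blocker position is checked by "switching between normal ventilation and single-lung ventilation (right and left lung will be tested independently"; each step is marked on the device beforehand. The anaesthetist is asked to hold each lumen of the double-lumen tube (DLT) clamped for at least 1 minute. No duration per side is given for a bronchial blocker.
- **Question (Protocol 7.2).** The secondary efficacy question is "whether EIT can correctly differentiate between normal and single-lung ventilation". The criterion is spelled out as "i.e. that EIT detects ventilation vs. no ventilation in each lung".
- **Size (Protocol 7.1).** With α = 0.05, "and a power = 0.9 in a two-sided testing resulted in a sample size of 22 patients", on the basis that "a difference of 0.1 of the proportion between reference and investigated variable shall be detected". With 15% "potential drop-outs 25 patients shall be enrolled in this subgroup of the study".
- **Rating (SAP 5.6.1).** Three blinded raters judge from video which lung is ventilated: "The results are entered patient-related (pseudo-patient number) in the following table by the rater". The codes are 0 (cannot be judged), 1 (right lung ventilated) and 2 (left lung ventilated). The majority code goes into one 2x2 table against the documented side. Sensitivity is a/(a+b), specificity is d/(c+d), and the success rate is (a+d)/(a+b+c+d), with confidence intervals.
- **Video (SAP 7.3).** Step 2 reads "Identify relevant markers which are set prior and post the induction of one lung ventilation". The section between one PRE and one POST marker is kept and saved under the site and patient ID. The workflow does not say which single-lung phase this is.

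**The concern.** The protocol builds a within-patient comparison: the same thorax and belt, first one lung blocked and then the other. The rating, on its most natural reading, takes one of these phases from each patient and leaves the other out. Three things follow.

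1. Sensitivity (right-ventilated clips) and specificity (left-ventilated clips) are estimated in separate patients, so each has roughly half the available information.
2. The split between right and left depends on which phase ends up in the clip, and the SAP does not fix this. One rate could rest on far fewer patients than the other.
3. No patient is rated on both sides, so the rating cannot say in how many patients the display was right for each lung in turn.

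This matters because the rating is the only blinded regional evidence in the plan. The other OLV efficacy analysis repeats the primary method, which correlates global waveforms and cannot locate a side.

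**Working it through.** **Reproducing n = 22.** The protocol gives α = 0.05 two-sided, power 0.90 and a difference of 0.1 in a proportion, but no reference proportion. A one-sample exact binomial test with an assumed reference of 0.999 against 0.899 gives a minimum n of 22. At that n a single miss rejects, and the power is 1 − 0.899^22 = 0.904. Other references do not give 22: for example, 0.89 against 0.99 needs 49 and 0.80 against 0.90 needs 137. So 22 reads as the size for one proportion over all patients with a reference near 1. That reference is an assumption. (22/0.85 = 25.9, which rounds up to 26, not 25; this does not affect the point.)

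**Denominators.** With one code per patient, (a+b) + (c+d) equals the number of rated patients. The two denominators do not overlap and average exactly half: 22/2 = 11, or 25/2 = 12.5 if all 25 are evaluable.

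**Uncontrolled split.** If the side shown fell at random with probability 0.5 (an assumption), the 95% binomial range for one side is 6 to 16 of 22, or 8 to 17 of 25.

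**Precision.** Exact (Clopper-Pearson) 95% limits. With all n correct, the lower limit is 0.025^(1/n). With one error it is the p that solves n·p^(n−1)·(1−p) + p^n = 0.025.

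| Patients behind the side-specific rate | All correct | One error |
|---|---|---|
| 11 (one phase rated, even split of 22) | 0.025^(1/11) = 71.5% | 58.7% (10/11) |
| 22 (both phases rated) | 0.025^(1/22) = 84.6% | 77.2% (21/22) |

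At the ends of the random split, the all-correct limits are 0.025^(1/6) = 54.1% and 0.025^(1/16) = 79.4%.

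**Power per side.** With the same assumed reference and a true rate of 0.899, power at n = 11 is 1 − 0.899^11 = 0.69, against 0.90 at n = 22.

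**States recorded and states rated.** Protocol 6.4.2.2 yields three states per patient: both lungs, right only and left only. SAP 5.6.1 has codes for the last two but none for both lungs. The normal-versus-single-lung contrast in Protocol 7.2 is therefore not rated either.

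**The case against.** Several stronger readings are tempting, and the documents do not support them.

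- *The protocol's question about each lung goes unanswered.* Each code states the condition of both lungs, one ventilated and one blocked, and both directions can appear across patients. Protocol 7.2 speaks of the change from normal to single-lung ventilation. It does not demand a right-to-left switch within a patient.
- *A display that favours one side could pass unnoticed.* If 70% of clips happened to show one side (an assumed mix), a display stuck on that side would reach a 70% success rate. But sensitivity and specificity would then be 100% and 0%, and the SAP reports both. Only a set of clips from one side alone would hide it. That is unlikely, but the plan does not exclude it.
- *The second phase is never used.* Question 2 of the plausibility questionnaire (Protocol 23.2) asks whether the image shows the blocked side and can draw on either phase. It is optional, and bedside personnel are not blinded (Protocol 6.1.2), so it does not replace the rating.
- *Whoever cuts the video picks the convenient side.* SAP 7.3 does not say who cuts the clips or that anyone chooses. It simply lacks a rule.
- *Two usable phases exist in every patient.* The 1-minute clamp is a request and is worded for the DLT only.

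Two further objections carry weight. The success rate already uses all patients, so 22/22 gives its 84.6% lower limit under the present plan; and Protocol 7.3 sets no pass/fail criterion, so no planned threshold is missed. The SAP also does not expressly rule out several clips per patient, although the patient-level table, the single reference side and the file naming all point to one.

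**Conclusion.** The point holds as a cheap improvement and does not show that the analysis is invalid. As written, the rating most naturally takes one side per patient with no rule for which one. The side-specific rates then rest on about 11 patients each where 22 are available, which costs about 13 percentage points of the all-correct lower limit (84.6 − 71.5 = 13.1) and 18.5 with one error (77.2 − 58.7). No patient is assessed on both sides.

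The figures assume 22 evaluable patients, an even split, and two usable phases in each. A less even split makes the smaller side worse; patients with only one usable phase reduce the gain. If the sponsor always intended two clips per patient, the SAP still has to say so and handle the pairing.

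**What to change.** - **SAP 7.3.** For each OLV patient, cut one clip for each usable single-lung phase, identified by its marker. Give every clip its own random number and present the clips in random order. A patient with one usable phase contributes that clip only.
- **SAP 5.6.1.** Build the 2x2 table per clip. Report the right and left rates with exact intervals. Add the proportion of patients correct on both sides, among those with two clips, with an exact interval. Use a patient-clustered interval for the overall success rate. If every clip is correct, a variance-based clustered interval has zero width, and the exact both-sides interval should be quoted instead.
- **Normal versus single-lung.** Either add a two-lung clip with its own code, taken from the baseline already recorded, or state that this rating addresses side only. If the code is added, count a two-lung answer to a single-lung clip as wrong, and add a rule for three raters giving three different codes.

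**Cost.** SAP wording, and about 25 × 2 = 50 single-lung clips instead of 25 for the same three raters (25 × 3 = 75 with the two-lung clip). No new patients, procedures or recordings are needed. The downsides are more cutting and rating time, paired data, and a small risk that a rater recognises two clips as one patient and infers the second answer by elimination. Random order and the two-lung clip reduce that risk.

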| 
Endpoints of the Trial
 | 
Primary Endpoint
 
The capability of PulmoVista 500 for continuous monitoring of ventilation and its changes at different points in time during varying states of regional ventilation, the cross-correlation function (CCF) between global tidal impedance (EIT) waveforms and global tidal volume (ventilator) curves will be evaluated.
 
Secondary Endpoints
 
 - First secondary endpoint: To assess the capability of PulmoVista 500 to detect changes in regional ventilation by evaluating the cross correlation between impedance waveforms derived from PulmoVista 500 and volume curves derived from ventilator during one-lung-ventilation. - Assess that changes of tidal volumes induced by ventilator settings can be monitored by the "Trends view" (see chapter 23.2) - Assess that changes of the end-expiratory lung volumes (induced by e.g. PEEP changes, recruitment and suctioning maneuvers) can be monitored by "dEELI trend view" (see chapter 23.2) - Documentation of any safety events related to the use of PulmoVista 500 - Clinical helpfulness of PulmoVista 500 is proven if 
 • see attachments (chapter 23.1) clinical usability |
| 
Sample Size
 | 
 • 80 patients 
25 patients shall be enrolled in a subgroup of patients with one-lung-ventilation (OLV)
 |

| | |
|-----------------------------|--|
| Anticipated Duration | 
Relating to trial
 
First patient first visit: January 2017
 
Last patient last visit: September 2017
 
Relating to patient: 8 hours (+Safety Follow-up)
 |

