6.1.3 PRIMARY AND SECONDARY STUDY ENDPOINTS

PRIMARY STUDY ENDPOINT

The capability of PulmoVista 500 for continuous monitoring of ventilation and its changes at different points in time during varying states of regional ventilation, the cross-correlation function (CCF) between global tidal impedance (EIT) waveforms and global tidal volume (ventilator) curves will be evaluated.

SECONDARY STUDY ENDPOINTS

- First secondary endpoint: To assess the capability of PulmoVista 500 to detect changes in regional ventilation by evaluating the cross correlation between impedance waveforms derived from PulmoVista 500 and volume curves derived from ventilator during one-lung-ventilation.
- Assess that changes of tidal volumes induced by ventilator settings can be monitored by the "Trends view"
- Assess that changes of the end-expiratory lung volumes (induced by e.g. PEEP changes, recruitment and suctioning maneuvers) can be monitored by "dELLI trend view"

- Documentation of any safety events related to the use of PulmoVista 500
- Assessing the use specific clinical helpfulness of PulmoVista 500 - clinical helpfulness of PulmoVista 500 is proven if
 - see attachments (chapter 23.1) clinical usability

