23.2 Clinical Plausibility Questionnaire

Questions addressing the regional aspects of the secondary endpoints

One of the major purposes of the pivotal clinical study

Assessment of the capability of PulmoVista 500 to continuously monitor changes of ventilation over time is to assess the plausibility of the regional information, which cannot be validated by CT scans.

The following questions are intended to validate, whether

- the regional information provided by PulmoVista 500 is plausible in the presence of certain lung conditions, which are visible in CXR or lung CT and known to cause poor ventilation
- PulmoVista 500 is capable of displaying changes of lung conditions induced by therapeutic interventions
- those changes are plausible and correspond to the information that an experienced user would expect based on his knowledge about lung physiology

Please respond the following questions in eCRF if this does not interfere with your clinical routine.

1. Select the view „**Main**“.
Does the **Tidal Image** indicate poorly or non-ventilated lung regions and does this location approximately match with those regions, where CXR or lung CT shows either lung collapse, atelectasis or pleura effusion?

2. Select the view "**Main**" and observe the Tidal Image, while one of the lungs is blocked.
Does the **Tidal Image correctly** indicate which side of the lung is not being ventilated?
3. Open the view "**dELLI trend**" after the PEEP setting has been changed. Set C1 at the lower and C2 at the higher PEEP level.
Does the image dELLI: C2 minus C1 show the expected increase of endexp.lung volume in turquoise (light blue) color?
4. Open the view "**End-insp. trend**" after the PEEP setting has been changed significantly (2 mbar or more). Set C1 at the lower and C2 at the higher PEEP level.
Does the image Change: C2 minus C1 and/or the corresponding regional Tidal Variations show the expected redistribution of ventilation from ventral to dorsal?
5. Open the view "**dELLI trend**" after lung suction has been conducted. Set C1 at a phase before and C2 during or immediately after the lung suction.
Does the image dELLI: C2 minus C1 show the expected decrease of lung volume in orange color?
6. Select the view "**Main**" and observe the Tidal Image from a patient with pneumonectomy.
Does the Tidal Image properly indicate the non-ventilated lung regions and does the location approximately match with those region, where the lung has been removed?

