3.3 SECUNDARY STUDY OBJECTIVES

3.3.1 Efficacy

- To demonstrate the ability of PulmoVista 500 to display regional ventilation changes, a quantitative evaluation is performed using the cross-correlation coefficient between the impedance waveforms of PulmoVista 500 and the ventilator volume waveforms in the subgroup of OLV patients.
- To evaluate Pulmo Vista 500's monitoring features, it assesses whether changes in tidal volumes induced by ventilation settings are represented by the "main view". For this purpose, the plausibility questionnaire is evaluated.

- Assess that changes of the end-expiratory lung volumes (induced by e.g. PEEP changes, recruitment and suctioning maneuvers) can be monitored by “dEELI trend view”. The plausibility questionnaire is also evaluated for this.
- To evaluate the clinical usefulness of PulmoVista 500, the questionnaire on clinical utility across all patients is evaluated.
- In order to demonstrate the ability of PulmoVista 500 to produce controlled induced regional changes, an evaluation is performed using the OLV subgroup. Three blinded rater evaluate the corresponding waveforms.

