From this table, the success rate $(a + d) / (a + b + c + d)$, the sensitivity $a / (a + b)$, the specificity $d / (c + d)$ and the corresponding confidence intervals are calculated. The reverence (real side of the ventilation) is taken in the study documentation (e.g. Name of corresponding Marker and/or MACRO Database) of the individual patients.

- To assess the ability of PulmoVista 500 to display changes in ventilation-induced tidal volumes through the "Trend View", the plausibility questionnaire across all patients is evaluated. The questions of the plausibility questionnaire in relation to the "main view" are individually counted according to their categories (yes / no / n.a.) and listed as a percentage.
- To assess the ability of PulmoVista 500 to display changes in end-expiratory lung volumes (induced by e.g. PEEP changes, recruitment and suction maneuvers) using the "dELLI Trend View", the plausibility questionnaire is evaluated across all patients. The questions of the plausibility questionnaire in relation to the "dELLI trend view" are individually counted according to their categories (yes / no / n.a.) and listed as a percentage.
- The evaluation of clinical usefulness, the nine questions of the questionnaire on clinical usefulness, are individually counted according to their category level (1 very difficult ... to ... 5 very useful) and listed on a percentage basis. Furthermore, the mean and standard deviation are calculated for each of these nine questions.

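### The SAP answers the tidal-volume-change endpoint by counting questionnaire items that ask neither about tidal volume nor about a change

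*SAP*

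**What the plan says.** The endpoint appears in four places, and the name of the view changes between them.

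- Protocol 1.2 (Synopsis): "Assess that changes of tidal volumes induced by ventilator settings can be monitored by the 'Trends view' (see chapter 23.2". The cross-reference is to the plausibility questionnaire.
- Protocol 6.1.3: "Assess that changes of tidal volumes induced by ventilator settings can be monitored by the" Trends view, without the cross-reference.
- SAP 3.3.1: "it assesses whether changes in tidal volumes induced by ventilation settings are represented by the" main view, to be judged from the plausibility questionnaire.
- SAP 5.6.1 opens with the trend view ("To assess the ability of PulmoVista 500 to display changes in ventilation-induced tidal volumes through the" Trend View). It then specifies the analysis for the other view: "The questions of the plausibility questionnaire in relation to the 'main view' are individually counted according to their categories", as yes / no / n.a. with percentages.

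Three items in protocol 23.2 use the main view. Item 1 asks whether the Tidal Image does "indicate poorly or non-ventilated lung regions and does this location approximately match with those regions" that are abnormal on chest X-ray or CT. Item 2 asks whether it does correctly "indicate which side of the lung is not being ventilated" while one lung is blocked. Item 6 concerns pneumonectomy: "Does the Tidal Image properly indicate the non-ventilated lung regions and does the location approximately match" the site of the removed lung.

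The primary cross-correlation coefficient (CCF) is defined in SAP 5.5 and 7.2. One artefact-free minute before the intervention and one after are exported, each is correlated on its own, and the two coefficients are averaged.

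**The concern.** An analyst who follows SAP 5.6.1 as written would report percentages on atelectasis, blocked side and pneumonectomy site as the result for tidal-volume change. Those are legitimate plausibility questions, but they are not this endpoint.

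The mismatch matters because the primary objective (protocol 5.1.1) covers ventilation and its changes, and protocol 7.2 attaches a conclusion about long-term monitoring to the CCF. If the tidal-volume-change endpoint is in effect unanswered, a reader may take the CCF as evidence that the device follows such changes. It is not built to show that.

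**Working it through.** **Step 1. Map the six plausibility items (protocol 23.2).**

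| Item | View | Asks about | Before/after? | Tidal-volume change? | Counted in SAP 5.6.1 under |
|---|---|---|---|---|---|
| 1 | Main | match with X-ray/CT findings | no | no | tidal-volume endpoint |
| 2 | Main | side blocked | no | no | tidal-volume endpoint |
| 3 | dEELI trend | end-expiratory volume after PEEP change | yes | no | end-expiratory endpoint |
| 4 | End-insp. trend | ventral-to-dorsal redistribution after PEEP change | yes | regional tidal variations only | nothing |
| 5 | dEELI trend | end-expiratory volume after suction | yes | no | end-expiratory endpoint |
| 6 | Main | site of pneumonectomy | no | no | tidal-volume endpoint |

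Three of 6 items are assigned to the endpoint. Of those 3, 0 are before/after and 0 mention tidal volume. Of all 6, 0 ask whether a change in global tidal volume is shown.

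**Step 2. Look elsewhere in the questionnaires.** Usability items 3 to 6 (protocol 23.1) use the End-insp. trend, and SAP 5.6.1 tabulates them. They rate ease or usefulness, not whether the display is correct.

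**Step 3. Check whether the CCF covers the change.** Within one file let impedance be Z = a + gV, with V the ventilator volume and g > 0 constant over that minute. Then corr(Z, V) does not depend on a or g. If g differs between the pre and post files, neither coefficient moves, and so neither does their mean.

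Now add noise with SD equal to k times the signal SD, so that r = 1/√(1 + k²). Calibrating to the 0.984 example in SAP 7.7 gives k = √(1/0.984² − 1) = 0.181. Suppose tidal volume is halved after the intervention and all breaths within a minute are equal:

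- Change missed (EIT amplitude and noise as before): post r = 0.984; mean 0.984.
- Change tracked, noise proportional to signal: post r = 0.984; mean 0.984.
- Change tracked, noise fixed: k doubles to 0.362, post r = 1/√(1 + 0.131) = 0.940; mean (0.984 + 0.940)/2 = 0.962.

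In the last case the device that misses the change scores higher than the one that tracks it. Simulation with breath-to-breath variation (CV 0 to 30%) gives the same picture: 0.984–0.986 for a pure gain error, 0.984–0.987 tracked with proportional noise, 0.962–0.968 tracked with fixed noise. A second simulation assumes 500 to 300 mL, 15 breaths a minute and 3% noise, a true post/pre ratio of 0.60. Device ratios of 0.60, 0.99, 1.41 and 0.20 all gave an averaged CCF of 0.995.

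**Step 4. Limit of step 3.** The cancellation needs a gain that is constant within the minute. If EIT amplitude fails to follow individual breaths, the CCF does fall: in simulation to about 0.97–0.98 at breath CV 10%, 0.93–0.95 at 20% and 0.86–0.92 at 30%, depending on the assumed breath shape.

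**Step 5. The plan's own figures.** The documents give no figure for this endpoint. As background, the primary sample size reproduces: d = 0.1/0.25 = 0.4, two-sided α = 0.05, one-sample t-test, n = 68 (power 0.902), and 68/0.85 = 80. With that SD and n, the test against zero rejects once the mean CCF exceeds 1.996 × 0.25/√68 ≈ 0.06, so none of the values above would alter it.

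**Step 6. Precision of a direct comparison.** Assume a Pearson r of 0.8 between log post/pre ratios, slope 1, and SD of the log volume ratio 0.3. The CI for r is tanh(atanh 0.8 ± 1.96/√(n − 3)). Residual SD = 0.3 × √(1/0.8² − 1) = 0.225, and the slope half-width is t(n−2) × 0.225/(0.3 × √(n − 1)).

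| n | 95% CI for r | slope half-width |
|---|---|---|
| 10 | 0.34–0.95 | 0.58 |
| 20 | 0.55–0.92 | 0.36 |
| 40 | 0.65–0.89 | 0.24 |

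These intervals are for Pearson r, not for a concordance coefficient.

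**The case against.** The best defence is that SAP 5.6.1 contains a labelling slip: main view was written where the end-inspiratory trend view, and so item 4, was meant. Item 4 is before/after, follows a change in a ventilator setting, and cites regional tidal variations; the questionnaire itself says that it addresses regional aspects. This stands in part. A reader might infer that no reassignment of items could help; the documents do not support that, since moving item 4 under this endpoint is a real, if partial, repair. It remains partial because the item asks about redistribution and not about the size of tidal volume.

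Second, the plan does examine change elsewhere. Items 3 and 5 compare end-expiratory volume before and after, and the three-rater OLV table tests which lung is ventilated. A reader might infer that the objective's reference to changes rests on the CCF alone; it does not. None of these, however, concerns tidal volume.

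Third, the CCF follows the primary endpoint as protocol 6.1.3 defines it. That stands. Step 3 is no case against the primary analysis, only against using it to stand in for this endpoint. Nor is the CCF blind to every tracking failure, as step 4 shows.

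Fourth, the endpoint concerns what the display shows, whereas amplitude ratios test the exported signals behind it. That also stands and has to be stated with any such analysis.

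**Conclusion.** The concern holds for the analysis of one named secondary endpoint. The three items counted for it do not measure it, the nearest item is left out of every tabulation, and no analysis in the plan compares the pre-to-post change in impedance amplitude with that in ventilator volume.

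The consequence is limited. The endpoint is descriptive, protocol 7.3 defines no pass/fail criterion, and the primary test is unaffected. What is lost is support for any statement that tidal-volume changes can be monitored. It would go too far to conclude that the primary analysis is invalid or that the trial has no evidence on change.

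The item count rests on the documents alone. The cancellation argument assumes one constant gain per exported minute. The simulated values are illustrative: SAP 7.7 does not say which recording its 0.984 example comes from, and breath shapes and noise were assumed. The conclusion does not depend on them. This should be corrected before analysis.

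**What to change.** **(a) Wording and tabulation.** Reconcile the view named in SAP 3.3.1 and 5.6.1 with protocol 1.2 and 6.1.3. Report items 1, 2 and 6 as regional plausibility only. Tabulate item 4 as the trend-view item on regional redistribution, and state that it covers the endpoint only in part.

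**(b) Supplementary descriptive analysis.** From column C (global impedance) and column N (ventilator volume) of the files already exported under SAP 7.2, compute the post/pre ratio of mean breath amplitude for each signal, with breaths delimited on column N. Include patients with both windows and a volume change above a threshold fixed in the SAP before analysis (10% is an assumed example), using one definition for ICU and OLV patients. List separately the one-window patients whom SAP 5.5 allows. Show a scatter plot and listing; add slope and concordance of the log ratios with 95% CIs if enough patients qualify (20 is an assumed minimum).

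**(c) Conclusion.** Keep the CCF as the primary analysis and limit what is drawn from it to waveform agreement within each ventilation state.

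**Cost.** SAP text and a short script; no new measurements. The analysis tests the signals and not the display. EIT sees one electrode plane (protocol 2.4), so the impedance-to-volume ratio can shift with redistribution or PEEP, and poor agreement would not by itself show device failure. The number eligible is unknown, because several listed interventions need not change tidal volume; with 10 to 20 patients step 6 shows wide intervals. Concordance also depends on the spread of volume changes among those selected, so it should be read together with the slope and the plot.
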